6. TREATMENTS

6.1. Study drug and dosage. Participants randomized to active treatment will receive cholecalciferol (vitamin D₃) 2000 IU capsules daily (Carlson Labs, Arlington Heights, Illinois). Cholecalciferol is the most commonly used vitamin D supplement and can be purchased over the counter. The 2000 IU daily dosage meaningfully increases vitamin D stores, lowers circulating PTH concentrations, and can be safely added to pre-existing vitamin D supplements and usual dietary vitamin D intake while remaining safely below the tolerable upper intake (4000 IU daily) defined by the Institute of Medicine. Moreover, the 2000 IU dosage of cholecalciferol is currently used in ongoing vitamin D treatment trials, enhancing the applicability of this study.

6.2. Placebo. Participants randomized to placebo will receive identically appearing softgel capsules, which contain sunflower oil in gelatin/glycerin/water (Carlson Labs).

6.3. Duration. The 16-week treatment duration will reliably raise serum 25(OH)D concentrations, the accepted measure of vitamin D stores, to their steady state concentrations.

6.4. Adherence. Adherence will be assessed by participant return of unused treatment at the end of the 16-week study period.

6.5. Discontinuation. Participants will be withdrawn from the study drug if they experience a significant adverse reaction related to the study drug or an intolerable adverse reaction, such as a persistent allergy or rash, or if the patient withdraws consent. Premature termination of this clinical trial may also occur due to a regulatory authority decision, drug safety problems as determined by the Data Safety Monitoring Board (DSMB), or at the discretion of the funding agency (NHLBI).

7. OUTCOMES

7.1. *Change in serum 1,25(OH)₂D concentration.* 1,25(OH)₂D is the active vitamin D hormone that mediates biological effects through binding to the intracellular vitamin D receptor. The conversion of cholecalciferol to 1,25(OH)₂D and catabolism of 1,25(OH)₂D proceed through a series of metabolic steps that plausibly vary across individuals. Serum 1,25(OH)₂D will be measured at baseline and 16-weeks using our established high performance liquid chromatography-tandem mass spectrometry assay.

7.2. *Change in serum PTH concentration.* PTH is a classic response marker for vitamin D. PTH gene expression is directly suppressed by 1,25(OH)₂D and is variably suppressed by cholecalciferol, providing an ideal opportunity to assess potential genetic, biomarker, and clinical characteristics that explain differences in the response to cholecalciferol treatment. Serum PTH will be measured at baseline and 16-weeks using an automated two-site sandwich immunoassay.

7.3. *Change in blood pressure.* 1,25(OH)₂D directly suppresses the expression of renin and lowers blood pressure in experimental models. However, in humans, cholecalciferol treatment has variable effects on blood pressure, with no net difference observed in a recent clinical trial. We will explore inter-individual differences in blood pressure response to cholecalciferol treatment as a clinically relevant study outcome among a subset of study participants who are either (1) not taking anti-hypertensive medications, or (2) report no changes in anti-hypertensive medications over the 16-week study period. Three systolic and diastolic blood pressures will be obtained five minutes apart using an automated cuff with the participant seated. The average of the last two measurements will be used for analysis.

7.4. *Change in urine and serum calcium concentrations.* Vitamin D increases gastrointestinal calcium absorption. Some of the absorbed calcium deposits within bones and extraosseous tissues, but the majority is excreted in the urine. We will evaluate changes in urinary calcium excretion and serum calcium concentrations as safety outcomes and we will investigate genetic, biomarker, and clinical characteristics that may modify the effect of cholecalciferol treatment on these outcomes. Spot urine calcium to creatinine ratios, a marker of urinary calcium excretion, and serum calcium concentrations will be measured at baseline and 16-weeks using a Beckman-Coulter clinical chemistry analyzer.

8. STUDY PROCEDURES

8.1. *MESA Exam 6.* For MESA Classic participants, baseline data and biosamples for this clinical trial will be obtained from existing procedures that are performed at MESA Exam 6. MESA-INVITe will use some of the MESA Exam 6 baseline data and biosamples, in accordance with the scientific aims and informed consent of the overall MESA study. Types of data that are collected as part of MESA exam 6 that may be used for MESA-INVITe include:

- Demographic information
- Medical and surgery histories
- Social habits (smoking and alcohol use)
- Prescription and non-prescription medication use
- Anthropomorphic measurements (height and weight)
- Blood pressure measurements
- Blood and urine collection

- DNA and RNA collection for epigenomic and transcriptomic analysis

Site investigators at each included MESA field center are co-investigators on this trial. The MESA exam 6 study visits are scheduled from September 2016 - March 2018. Study personnel will mail materials explaining the goals and procedures of this trial to MESA participants and will call participants prior to their Exam 6 visit to review eligibility. At the time of Exam 6, or soon after Exam 6, study personnel will approach potentially eligible subjects, confirm eligibility criteria, explain the details of the trial, and answer relevant questions. The MESA coordinating center will match all medications and supplements reported in the inventory to a known list of vitamin D containing medications in real time to determine the amount of current vitamin D use. For participants who are found to be suitable and interested in this study, MESA personnel will obtain informed consent, consult the MESA Coordinating Center for randomization, and distribute the study medication.

Participants who are unable to use their regularly scheduled Exam 6 as the baseline visit for MESA-INVITe (for example because study staff were unable to start MESA-INVITe at the scheduled Exam 6, or the participant elected to reduce their current vitamin D supplement use [Section 4]) may complete a separate “Exam 6-plus” to collect baseline MESA-INVITe measurements and dispense study medication. All MESA Family and Air participants will use Exam 6-plus visits for basement measurements. In these cases, “Exam 6-plus” will include informed consent, a medical history focused on MESA-INVITe eligibility criteria, vital signs measurement, phlebotomy, urine collection, and study drug dispensing.

Participants in MESA INVITe will be contacted by telephone approximately two weeks after Exam 6 (or 6-plus) to address any participant questions regarding the study, encourage adherence to the study drug, and confirm scheduling for MESA Exam 6a.

8.2. MESA Exam 6A. We will ask enrolled trial participants to return to their respective MESA field centers for a specialized examination specific to this trial approximately 16-weeks after their Exam 6 (or 6-plus) visit. This follow-up visit is denoted as “MESA exam 6A.” Study personnel will encourage participants to return as close to their 16-week follow-up time as possible, within +/- 4 weeks. Study medication bottles include 20 weeks of medication and participants will be asked to continue to take their medication up until the time of their exam 6A visit.

The trial will make every effort to follow the intention-to-treat principle of clinical trials, in which all participants who enter a trial are included in the analysis. Therefore, there are no time limitations for the exam 6A visit- it is better to bring a participant back after 30 weeks than not at all, even if the participant has stopped taking the study medication.

The Exam 6A study visit is expected to last approximately 60 minutes and will include the following components:

- Return of unused study medication to assess compliance during the trial
- Measurement of end-of-study systolic and diastolic blood pressures
- Completion of an end-of-study medication inventory, including the use of vitamin D-containing medications (both prescribed and over the counter)
- Completion of brief questionnaire to assess sunlight exposure during the trial
- Collection of end-of-study blood and spot urine specimens

- Collection of end-of-study DNA and RNA for future assessment of changes in gene expression with vitamin D treatment.

MESA study coordinators will count and record all unused study medication. Measurements of systolic and diastolic blood pressures, completion of the medication inventory, and collection of blood and spot urine specimens will be performed using identical procedures to those used for MESA Exam 6.

The primary outcomes of this trial are changes in serum concentrations of parathyroid hormone (PTH), calcitriol, and urinary calcium.

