10. ANALYTIC PLAN

We will describe MESA participants screened, enrolled, and completing this ancillary study according to CONSORT guidelines and compare characteristics of participants who do and do not pass through each of these stages. Primary analyses will include participants who complete baseline and 16-week follow-up regardless of adherence. Secondary analyses will include all consented participants using multiple imputation to address data missing from the 16-week follow-up visit.

We will construct linear models for the follow-up value of each outcome variable to determine whether common and rare polymorphisms in six candidate genes modify vitamin D₃ treatment effects: *CYP2R1*, *CYP24A1*, *CYP27B1*, *CYP3A4*, *SULT2A1*, and *VDR*. Independent variables in the model will include treatment group, number of minor alleles at a given locus, the interaction between treatment group and number of minor alleles, the baseline value of the outcome variable, and the following preselected precision variables: age, gender, BMI, season, and the estimated glomerular filtration rate (GFR). Given sample size limitations we will conduct primary genetic analyses among only the white and Black subgroups with potential associations carried to the Chinese and Hispanic groups. Power to detect genetic associations of common variants are shown in Table 1. Secondary genetic analyses are planned to explore all measured and imputed genetic variants with >5% minor allele frequency derived from the Affymetrix 6.0 chip and 1000 Genomes imputation using the regression framework described above.

Table 1. Power for analyses of common variants.

Minor allele frequency	All	White	Black
0.1	0.013	0.001	0.001
0.2	0.141	0.013	0.006
0.3	0.357	0.045	0.021
0.4	0.521	0.083	0.041

We will test whether race/ethnicity, gender, body mass, index, estimated GFR, and serum concentrations of 25(OH)D, bioavailable 25(OH)D, and 24,25(OH)₂D₃ modify the response to vitamin D₃ treatment using analogous regression models to those described above.

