Brief statement of the problem

The Individualized Response to Vitamin D Treatment (INVITE) trial was designed to identify clinical, genetic, and biomarker differences across individuals in response to cholecalciferol therapy. The trial was originally conceived to address two emerging research directions within the National Heart Lung and Blood Institute (NHLBI):

1. Innovative use of existing observational cohort studies to include nested clinical trials
2. A personalized medicine approach that includes testing individualized responses to treatments, including clinical and genetic characteristics.

The INVITE trial is nested within the NHLBI sponsored Multi-Ethnic Study of Atherosclerosis (MESA). Participants are recruited from four MESA clinical sites at the time of their 6th examination. Recruitment for the INVITE trial has been lower than anticipated due to:

[figure not shown]
1. Overall turnout for MESA Exam 6 was considerably lower than expected, particularly at the Wake Forest site, which is a primary INVITE recruitment site.
2. The INVITE grant was funded after MESA Exam 6 was already underway.
3. The use of high-dose cholecalciferol supplementation was greater than expected.

We have implemented several procedures to increase recruitment, including the creation of specialized visits for participants who already completed MESA Exam 6, the inclusion of an optional washout period for pre-existing vitamin D users, and the addition of a 5th MESA recruitment site. Each of these procedures have increased enrollment; however, the final anticipated sample size will be 682.

Changes to enrollment

As of September 1, 2018, the MESA INVITE study had enrolled 523 participants. We now plan to enroll 682 participants by January 18, 2019, at which time we will close enrollment. We are currently on track to meet this goal based on the current rate of recruitment (below). With 16 weeks of scheduled follow-up for each participant, we plan to complete all study visits by May 30, 2019.

Figure 1. Enrollment in MESA INVITE

Changes to the analytic plan

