The overall design of the study has not changed. INVITE remains a randomized two-arm, double-blind clinical trial with a 3:1 ratio of assignment to active vitamin D treatment versus placebo. We discussed the possibility of removing the placebo group to create a treatment only study; however, implementing such a change after recruitment of greater than 75% of participants would be difficult to explain to the DSMB, the MESA study sites, and the participants themselves. Moreover, we believe that such a change in design would diminish the impact of manuscripts resulting from this study.

Unlike typical event driven trials, INVITE seeks to identify characteristics that modify the response to treatment. To increase study power to detect such associations, we will start by evaluating only participants who are treated with active vitamin D to assess main effects of genetic polymorphisms and clinical characteristics on the changes in study outcomes. In parallel we will present analytic results from our original approach, in which we analyze all participants and test the interaction of relevant exposures with treatment assignment.

Changes to sample size and study power

Study power for the treatment only analytic approach is considerably greater than that of the original interaction-based analyses. Differences in the effect of vitamin D treatment on study outcomes of change in parathyroid hormone, 1,25-dihydroxyvitamin D, and urine calcium to creatinine ratios according to a modifying genetic polymorphism are presented below. Under the anticipated sample size of 682, the INVITE study will maintain power to detect clinically relevant associations. The INVITE DSMB, which includes a faculty biostatistician, met on September 13, 2018, at which time it reviewed and approved these changes to the analytic plan and power.

Figure2. Minimal detectable associations for genetic polymorphisms under a treatment-only analysis.

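### Exam 6A values from any time after week 20, including off drug, count as the 16-week outcome, and the treatment-only lead analysis has no in-window version

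*Combined protocol and SAP*

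**What the plan says.** Protocol Section 8.2 sets the target for the follow-up visit: "Study personnel will encourage participants to return as close to their 16-week follow-up time as possible, within +/- 4 weeks". It also says "Study medication bottles include 20 weeks of medication", and participants are to keep taking them until the visit. The next paragraph appeals to intention to treat and removes the limit: "there are no time limitations for the exam 6A visit- it is better to bring a participant back after 30 weeks". A late visit is preferred to none, which applies "even if the participant has stopped taking the study medication".

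Section 7 describes the laboratory outcomes as measured at baseline and 16 weeks. Section 10 defines the analysis set: "Primary analyses will include participants who complete baseline and 16-week follow-up regardless of adherence". The models adjust for the baseline value, age, gender, BMI, season and eGFR. They have no term for visit timing or time since last dose, and no in-window analysis is listed.

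The later Analytic Plan, under *Changes to the analytic plan*, changes which analysis leads: "we will start by evaluating only participants who are treated with active vitamin D". The interaction analysis in all participants is reported in parallel. No window is added for either.

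**The concern.** The 20-week supply ends at the top of the target window. Someone who takes the capsules daily and attends later has therefore run out by design, which differs from ordinary non-adherence. Section 6.3 justifies the 16-week duration by 25(OH)D reaching steady state, and a value taken weeks after the last capsule no longer fits that reasoning.

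In the randomised interaction analysis both arms attend under the same rule, and an all-visits result is a legitimate intention-to-treat answer. The treatment-only analysis has no placebo arm and attributes differences in change to genotype or clinical characteristics. A late, off-drug participant there can look like a poor responder. If lateness differs by a modifier such as race or eGFR, that can appear as modification.

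**Working it through.** The plan gives no figure of its own on this point to reproduce. Figure 2 (minimal detectable associations) is not shown in the available text.

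**Inputs from the documents.** Target 16 weeks, encouraged within 4 weeks either side; supply 20 weeks; no upper limit, with 30 weeks as the example (Section 8.2). Completers analysed regardless of adherence, with no timing term (Section 10). Active-arm analysis leads (Analytic Plan).

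**Not in the documents, so assumed.** *f* is the share of active-arm outcome values taken late and off drug. *r* is the share of the drug response still present at those visits.

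**Step 1: timing.** The window runs from 16 − 4 = 12 to 16 + 4 = 20 weeks, so its upper end equals the supply. With daily use, a 30-week visit falls 30 − 20 = 10 weeks after the last capsule.

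**Step 2: dilution.** Suppose lateness and retention are unrelated to the modifier, and β is the drug-related part of its slope. The expected slope over all visits is (1 − f)β + f·r·β = β[1 − f(1 − r)], so the proportional loss is f(1 − r):

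| f | r = 0.8 | r = 0.5 | r = 0 |
|---|---|---|---|
| 5% | 1% | 2.5% | 5% |
| 10% | 2% | 5% | 10% |
| 20% | 4% | 10% | 20% |

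This applies only to the drug-related part. A treatment-only slope also contains any effect of the characteristic on change that has nothing to do with the drug, and that part need not shrink.

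**Step 3: distortion.** Take two genotype groups with the same true response Δ.

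- Late shares f₁ and f₀, same r: the observed difference is −(f₁ − f₀)(1 − r)Δ. With f₁ = 20%, f₀ = 5% and r = 0 it is −0.15Δ; with the shares swapped it is +0.15Δ.
- Same f, retention r₁ and r₀: the difference is f(r₁ − r₀)Δ. With f = 20%, r₁ = 0.5 and r₀ = 0 it is 0.20 × 0.5 × Δ = 0.10Δ.

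The true difference is zero in every case.

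**Step 4: price of a window.** Dropping late values leaves 1 − f of the sample. If lateness is uninformative and residual variance is unchanged, dropping is more efficient when 1 − f > [1 − f(1 − r)]². At f = 20%:

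- r = 0: 0.80 against 0.80² = 0.64, so dropping is better.
- r = 0.5: 0.80 against 0.90² = 0.81, about equal.
- r = 0.8: 0.80 against 0.96² = 0.92, so keeping is better.

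Neither version wins throughout, which argues for reporting both.

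**The case against.** Accepting late visits is deliberate and openly reasoned. The Analytic Plan does not say that its treatment-only analysis is conditional on being on drug, so an on-treatment target is a reader's inference. This stands in part: an all-visits analysis is not wrong, but its result cannot by itself be read as response to treatment.

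It could also be argued that a 30-week visit is not 16-week follow-up and so falls outside the primary set. Section 8.2 ties late visits to including all participants in the analysis, so they appear meant to be used. If they are not, the plan needs to say so.

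A window is an imperfect remedy. It keeps participants who stopped drug but attended on time, discards visits before week 12, and selects on attendance after randomisation. All of this stands, and it is why the in-window result should sit beside the all-visits result and not replace it.

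Three stronger readings are tempting, and the documents do not support them.

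- *Every modifier slope shrinks toward zero.* This holds only if lateness and persistence are unrelated to the modifier. CYP24A1 is a candidate gene, and Section 7.1 says that catabolism of 1,25(OH)₂D plausibly varies between people, so a slope could also grow.
- *A definite loss of power.* The late share, the retained response and any baseline power for the treatment-only analysis would all have to be assumed.
- *The close-out date is an error.* The plan says "With 16 weeks of scheduled follow-up for each participant, we plan to complete all study visits by May 30, 2019". January 18, 2019 plus 20 weeks is June 7, which is 8 days after that date. But plus 16 weeks is May 10, with 20 days to spare. The 4-week margin is only encouraged, May 30 is a planning date, and 30 weeks is a last-resort example. Any fixed close-out limits the recovery of late attenders.

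**Conclusion.** The point holds as a gap in the analysis plan and not as a fault in collecting the data. Off-drug values from after week 20 enter the treatment-only lead analysis as 16-week responses, with nothing in the plan to separate them. The intention-to-treat reason given for accepting them does not carry over to an analysis without a randomised comparison.

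The effect may be negligible or material. Over the assumed ranges, dilution runs from about 1% of the slope (5% late, 80% retained) to 20% (20% late, none retained). Differential lateness or retention could move an association either way. These figures are illustrations and not estimates for this trial.

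**What to change.** - Keep bringing everyone back, and keep all visits in the randomised interaction analysis as the intention-to-treat result.
- For the treatment-only analysis, pre-specify a version limited to Exam 6A visits in weeks 12–20, the protocol's own window, and report it beside the all-visits result.
- Run the same in-window version for the interaction analysis.
- Report how many visits fell outside the window, so that readers can judge how much it matters.

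The cost is a few sentences in the Analytic Plan and one extra run of each model on data already collected. The in-window set will be slightly smaller and somewhat selected on attendance. It will still contain participants who stopped drug but attended on time, and the text should say so.

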9. ADVERSE EVENTS

Cholecalciferol is a commonly used over-the-counter supplement that has been evaluated in many published clinical trials using identical or similar dosing strategies to that proposed in this trial (eg, 50,000 IU monthly and 2400 IU daily). Previous trials have found no differences in the frequency of adverse events comparing cholecalciferol to placebo. Some studies have noted a small increase in serum and urine calcium concentrations, prompting the measurement of these characteristics in this study. One study found a small increase in the frequency of nephrolithiasis, presumably due to urinary calcium excretion, prompting our decision to exclude MESA participants who have a history of kidney stones.

9.1. Definitions. An adverse event (AE) is any untoward medical occurrence in a study participant regardless of its relationship to study treatment. A serious adverse Event (SAE) is any untoward medical occurrence that results in death, is life-threatening, requires hospitalization or prolongation of an existing hospitalization, results in persistent or significant disability, or is a congenital anomaly/birth defect. Important medical events that do not fall into the above categories may also be considered an SAE when, based on medical judgment, such events may jeopardize the patient's safety and require medical/surgical intervention to prevent one of the outcomes listed in the SAE definition. The term SAE is not intended as a measure of severity or intensity. All AE's/SAE's that occur after the time of informed consent will be reported.

A suspected adverse reaction is any adverse event for which there is a reasonable possibility that the drug caused the event. "Reasonable possibility" is typically defined as evidence to suggest a causal relationship between the drug and the adverse event. Suspected adverse reaction implies a lesser degree of certainty about causality than adverse reaction, which means any adverse event caused by a drug. An unexpected adverse event or unexpected suspected adverse reaction is an adverse event or suspected adverse reaction that is not listed in the investigator brochure or is not listed at the specificity or severity that has been observed; or, if an investigator brochure is not required or available, is not consistent with the risk information described in the general investigational plan.

9.2. Adverse Events Reporting. All AEs will be reported on the Adverse Events Form that will be completed by MESA field center staff during the study. Pre-existing conditions (any condition that was known to be present prior to signing of informed consent or identified during the screening procedures) will not be considered or recorded as AEs unless the condition worsens in intensity or frequency. The investigators will be responsible for reporting all AE's to the IRB and DSMB in a timely fashion.

9.3. Assessment of Causality and Severity. The seriousness of adverse events will be ascertained by the study staff and the need for further evaluation, follow-up, or referral. The relationship between study participation and AEs will be determined according to standard criteria:

- A. Not related – temporal relationship of the onset of the event, relative to study participation, is not reasonable or another cause can by itself explain the occurrence of the event.
- B. Possibly related – temporal relationship of the onset of the event, relative to study participation, is reasonable but the event could have been due to another, equally likely cause.
- C. Probably related – temporal relationship of the onset of the event, relative to study participation, is reasonable and the event is more likely explained by the study treatment than by another cause.
- D. Definitely related – temporal relationship of the onset of the event, relative to study participation, is reasonable and there is no other cause to explain the event.

